6.4.3 Exploratory Efficacy Endpoints

The exploratory efficacy endpoints are as follows:

- Rate of severe asthma exacerbations during the 48-week double-blind treatment period, defined as asthma symptoms requiring hospitalization or resulting in death attributed to asthma
- Absolute change from randomization in pre-bronchodilator FEV₁ (percentage predicted) at Week 50
- Absolute change from randomization in patient-reported daytime asthma symptom severity, as measured by a daily symptom diary (as defined in primary efficacy objective), at Week 50
- Absolute change from randomization in patient-reported nighttime asthma symptom severity, as measured by a daily symptom diary (as defined in primary efficacy objective), at Week 50
- Absolute change from randomization in patient-reported number of puffs of short-acting rescue inhaler or number of times nebulizer was used at Week 50
- Absolute and relative change from randomization visit in PD₂₀ as a measure of airway hyper-responsiveness at Week 30, in patients who consent to this optional assessment at select sites

Analysis of exploratory efficacy endpoints will be described in the DAP.

6.5 SAFETY ANALYSES

The safety analysis population will consist of all randomized patients who received at least one dose of study drug during the 48-week double-blind treatment period, with patients grouped according to treatment received (MTPS9579A or placebo). Safety analysis of run-in patients will consist of all patients who received the single-blind placebo dose during the run-in period, regardless of whether or not the patient is randomly allocated into the double-blind treatment period. For this safety analysis, only events that occur during the 2-week run-in period will be included and grouped together since all patients will have received placebo.

Safety will be assessed through summaries of adverse events, laboratory test results, ECG parameters, physical examination findings, and vital signs. Verbatim descriptions of treatment-emergent adverse events will be coded using the MedDRA thesaurus terms and their severity by WHO Toxicity Grading Scale (see [Appendix 7](#)), and their incidence will be summarized by treatment arm. A treatment-emergent adverse event is defined as any new adverse event reported or worsening of an existing condition on or after the first dose of study drug during the 48-week double-blind treatment period. In addition, separate summaries will be generated for serious adverse events, adverse events of special interest, deaths, pregnancies, malignancies, anaphylaxis events, adverse events leading to discontinuation from the study, and adverse events leading to discontinuation of study drug.

Clinical laboratory data (serum chemistry, hematology evaluations, and urinalysis values) and vital signs will be summarized by descriptive statistics for each treatment group.

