5.2.3 Adverse Events of Special Interest (Immediately Reportable to the Sponsor)

Adverse events of special interest are required to be reported by the investigator to the Sponsor immediately (i.e., no more than 24 hours after learning of the event; see Section [5.4.2](#) for reporting instructions). Adverse events of special interest for this study are as follows:

- Cases of potential drug-induced liver injury that include an elevated ALT or AST in combination with either an elevated bilirubin or clinical jaundice, as defined by Hy's Law (see Section [5.3.5.7](#))
- Suspected transmission of an infectious agent by the study drug, as defined below
 - Any organism, virus, or infectious particle (e.g., prion protein transmitting transmissible spongiform encephalopathy), pathogenic or non-pathogenic, is

considered an infectious agent. A transmission of an infectious agent may be suspected from clinical symptoms or laboratory findings that indicate an infection in a patient exposed to a medicinal product. This term applies only when a contamination of the study drug is suspected.

- Grade ≥ 3 allergic reaction within 24 hours of infusion or suspected to be due to study drug

Grade ≥ 3 allergic reactions include generalized urticaria and angioedema (Grade 3) and anaphylaxis (Grade 4).

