5.3.5.1 Infusion-Related or Injection Reactions

Adverse events that occur during or within 24 hours after study drug administration should be captured as individual signs and symptoms on the Adverse Event eCRF rather than an overall diagnosis (e.g., record dyspnea and hypotension as separate events rather than a diagnosis of infusion-related or anaphylactic reaction).

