Appendix 1: Schedule of Activities

	Screening ^a	Run-In ^b	Rand. ^c	Treatment															EOT ^d	Safety Follow -Up	Safety T/C ^e	UV ^f	ET ^g
Day (Window)	–28 to –1	1		15 (±2)	23 (±2)	44 (±3)	72 (±3)	100 (±3)	128 (±3)	156 (±3)	184 (±3)	212 (±3)	240 (±3)	268 (±3)	296 (±3)	324 (±3)	352 (±4)	380 (±3)	408 (±3)				
Week	–4 to 0	0	2	3	6	10	14	18	22	26	30	34	38	42	46	50	54	58					
Visit	1	2	3	4	5	6	7	8	9	10	11	12	13	14	15	16	17	18					
ACQ-5	x																						
Serum PK sample ^{aa}				x ^q	x	x	x	x		x		x		x		x	x		x	x			
Serum sample for biomarkers ^{bb}		x		x ^q	x	x		x			x					x				x			
Nasosorption for biomarkers ^{bb}		x		x ^q	x	x		x			x					x				x			
Urine sample for biomarkers ^{bb}		x		x ^q		x											x						
Serum ADA sample ^{bb, cc}				x ^q		x		x		x		x		x		x		x	x	x			
Blood for SNP ^{bb}				x ^q																			
Blood for WGS ^{bb, dd}				x ^q																			
Adverse events ^{ee}		x	x	x ^q	x	x	x	x	x	x	x	x	x	x	x	x	x	x	x	x			
Study drug administration ^{ff}		PBO		x ^q		x	x	x	x	x	x	x	x	x	x	x							
Inspection for infusion reaction(s)				x _{m,q}	x	x ^m	x	x	x	x													

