Appendix 6: Anaphylaxis Precautions and Diagnosis

Criteria for Anaphylaxis Diagnosis

Anaphylaxis is highly likely when any one of the following criteria are fulfilled (adapted from Sampson et al. 2006):

1. Acute onset of an illness (minutes to several hours) with involvement of the skin, mucosal tissue, or both (e.g., generalized hives, pruritis or flushing, swollen lips-tongue-uvula)

AND AT LEAST ONE OF THE FOLLOWING:

- a. Respiratory compromise (e.g., dyspnea, wheeze-bronchospasm, stridor, reduced PEF, hypoxemia)
 - b. Reduced BP or associated symptoms of end-organ dysfunction (e.g., hypotonia [collapse], syncope, incontinence)
2. Two or more of the following that occur rapidly after exposure to a likely allergen for that patient (minutes to several hours):
 - a. Involvement of the skin-mucosal tissue (e.g., generalized hives, itch-flush, swollen lips-tongue-uvula)
 - b. Respiratory compromise (e.g., dyspnea, wheeze-bronchospasm, stridor, reduced PEF, hypoxemia)
 - c. Reduced BP or associated symptoms (e.g., hypotonia [collapse], syncope, incontinence)
 - d. Persistent gastrointestinal symptoms (e.g., crampy, abdominal pain, vomiting)

Reference:

Appendix 7

WHO Toxicity Grading Scale

ITEM	Grade 1 Toxicity	Grade 2 Toxicity	Grade 3 Toxicity	Grade 4 Toxicity
HEMATOLOGY				
Hemoglobin	9.5–10.5 g/dL	8.0–9.4 g/dL	6.5–7.9 g/dL	< 6.5 g/dL
Absolute neutrophil count	1000–1500/mm ³	750–999/mm ³	500–749/mm ³	<500/mm ³
Platelets	75,000–99,000/mm ³	50,000–74,999/mm ³	20,000–49,000/mm ³	<20,000/mm ³
PT	1.01–1.25×ULN	1.26–1.5×ULN	1.51–3.0×ULN	>3×ULN
aPPT	1.01–1.66×ULN	1.67–2.33×ULN	2.34–3×ULN	> 3×ULN
Fibrinogen	0.75–0.99×LLN	0.50–0.74×LLN	0.25–0.49×LLN	< 0.25×LLN
Fibrin split product	20–40 µg/mL	41–50 µg/mL	51–60 µg/mL	> 60 µg/mL
Methemoglobin	5%–9.9%	10.0%–14.9%	15.0%–19.9%	> 20%
LIVER ENZYMES				
AST (SGOT)	1.25–2.5×ULN	2.6–5×ULN	5.1–10×ULN	> 10×ULN
ALT (SGPT)	1.25–2.5×ULN	2.6–5×ULN	5.1–10×ULN	> 10×ULN
GGT	1.25–2.5×ULN	2.6–5×ULN	5.1–10×ULN	> 10×ULN
ALP	1.25–2.5×ULN	2.6–5×ULN	5.1–10×ULN	> 10×ULN
Amylase	1.1–1.5×ULN	1.6–2.0×ULN	2.1–5.0×ULN	> 5.1×ULN
CHEMISTRIES				
Hyponatremia	130–135 mEq/L	123–129 mEq/L	116–122 mEq/L	< 116 or mental status changes or seizures

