## Output 4.7 Adverse Events (AET02)

Protocol: GB41149

Analysis Population:

- (1) Placebo Run-in Period; Run-in safety-evaluable population (PERIOD1\_PEFL)
- (2) 48-Week Double-Blind Treatment Period and 12-Week Safety Follow-up Period; Safety-evaluable population (PERIOD2\_SE)
- (3) 3 patients that were administered saline by IV infusion without IP at week18 visit (DEVI)
- (4) Grade 3+ adverse events (GRD3)

MedDRA System Organ Class MedDRA Preferred Term	Placebo (N = XXX)	MTPS9579A Active (N = XXX)	All Patients (N = XXX)
Total number of patients with at least one adverse event	nn (xx.x%)	nn (xx.x%)	nn (xx.x%)
Overall total number of events	nn	nn	nn
SOC 1			
Total number of patients with at least one adverse event	nn (xx.x%)	nn (xx.x%)	nn (xx.x%)
Total number of events	nn	nn	nn
PT 1	nn (xx.x%)	nn (xx.x%)	nn (xx.x%)
PT 2	nn (xx.x%)	nn (xx.x%)	nn (xx.x%)
PT 3	nn (xx.x%)	nn (xx.x%)	nn (xx.x%)
PT 4			
...			

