## Output 4.15 Adverse Event of Special Interest Summary Table (AET01\_AESI)

Protocol: GB41149

Analysis Population:

- (1) Placebo Run-in Period; Run-in safety-evaluable population (PERIOD1\_PEFL)
- (2) 48-Week Double-Blind Treatment Period and 12-Week Safety Follow-up Period; Safety-evaluable population (PERIOD2\_SE)

	Placebo (N = XXX)	MTPS9579A Active (N = XXX)	All Patients (N = XXX)
Total number of patients with at least one AE	nn (xx.x%)	nn (xx.x%)	nn (xx.x%)
Total number of AEs	nn	nn	nn
Total number of patients with at least one AE by worst grade			
Grade 1	nn (xx.x%)	nn (xx.x%)	nn (xx.x%)
Grade 2	nn (xx.x%)	nn (xx.x%)	nn (xx.x%)

Grade 3	nn (xx.x%)	nn (xx.x%)	nn (xx.x%)
Grade 4	nn (xx.x%)	nn (xx.x%)	nn (xx.x%)
Total number of patients with study drug withdrawn due to AE	nn (xx.x%)	nn (xx.x%)	nn (xx.x%)
Total number of patients with dose modified/interrupted due to AE	nn (xx.x%)	nn (xx.x%)	nn (xx.x%)
Total number of patients with treatment received for AE	nn (xx.x%)	nn (xx.x%)	nn (xx.x%)
Total number of patients with all non-fatal AEs resolved	nn (xx.x%)	nn (xx.x%)	nn (xx.x%)
Total number of patients with at least one unresolved or ongoing non-fatal AE	nn (xx.x%)	nn (xx.x%)	nn (xx.x%)
Total number of patients with at least one serious AE	nn (xx.x%)	nn (xx.x%)	nn (xx.x%)
Total number of patients with at least one related AE	nn (xx.x%)	nn (xx.x%)	nn (xx.x%)

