### Analysis Population:

- (1) Placebo Run-in Period; Run-in safety-evaluable population (PERIOD1\_PEFL)
- (2) 48-Week Double-Blind Treatment Period and 12-Week Safety Follow-up Period; Safety-evaluable population (PERIOD2\_SE)
- (3) 3 patients that were administered saline by IV infusion without IP at week18 visit (DEVI)

Treatment: <Treatment>

Center/Patient ID	Study Day at Onset	Time from Last Dose to Onset	AE Duration in Days	Most Extreme Intensity	Cause d by Study Drug	Outcome (1)	Treatment for AE	Action Taken (2)
Adverse Event MedDRA Preferred Term	Age/Sex/Race	days hrs mins	Serious					
ANEAMIA NOS	xxx*	xxx xx xx	1**	No	Mild	Yes	2	No
APPETITE DECREASED	xxx	xxx xx xx	2	No	Moderate	No	3	No
DIARRHEA NOS	xxx	xxx xx xx	2**	No	Mild	No	3	No

(1) Outcome: 1 = fatal; 2 = not recovered/not resolved; 3 = recovered/resolved; 4 = recovered/resolved with sequelae; 5 = recovering/resolving; 6 = unknown.

(2) Action taken: 1 = dose increased; 2 = dose not changed; 3 = dose reduced; 4 = drug interrupted; 5 = drug withdrawn; 6 = not applicable; 7 = unknown.

\* Study day derived from imputed onset date

\*\* Duration derived from imputed onset date and/or end date

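### The protocol promises a separate summary of anaphylaxis events; the SAP has no such output, and its term tables and pooled AESI table do not give a count of cases by arm

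*Protocol*

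**What the plan says.** Protocol 6.5 lists the adverse-event summaries to be produced: "separate summaries will be generated for serious adverse events, adverse events of special interest, deaths, pregnancies, malignancies, anaphylaxis events", followed by events leading to discontinuation. Anaphylaxis is a separate item from AESIs in that list.

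Protocol 5.3.5.1 governs how reactions are entered. For events during an infusion or in the 24 hours after it, sites enter individual signs, and the example given is to "record dyspnea and hypotension as separate events rather than a diagnosis of infusion-related or anaphylactic reaction". Protocol 5.4.2.2 places AESI reports on the same Adverse Event eCRF.

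Protocol Appendix 6 supplies a case definition: "Anaphylaxis is highly likely when any one of the following criteria are fulfilled". Its criteria require signs from different organ systems in one acute episode.

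Protocol 5.2.3 defines three kinds of AESI: potential drug-induced liver injury by Hy's Law, suspected transmission of an infectious agent, and a Grade 3 or higher "allergic reaction within 24 hours of infusion or suspected to be due to study drug". Anaphylaxis is the Grade 4 form of the third.

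In the SAP, Output 4.7 tabulates system organ class and preferred term, with "48-Week Double-Blind Treatment Period and 12-Week Safety Follow-up Period; Safety-evaluable population" as its main analysis set. Output 4.15 summarises AESIs by arm, with rows such as "Total number of patients with at least one AE by worst grade" and rows for action taken and outcome. Listing 4.32 has a column "Time from Last Dose to Onset".

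**The concern.** Hypersensitivity and infusion-related reactions are the risks that Protocol 5.1.1 names for this antibody. The protocol defines anaphylaxis, trains investigators to recognise it, schedules inspection for infusion reactions and promises a summary. What is missing is the last step, a planned count of patients per arm.

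The omission matters more here than a missing table usually would, because of the recording rule. If sites entered the diagnosis, the count could be read from a preferred-term row in Output 4.7. Since they are told to enter the signs, that row would not be expected to hold infusion-related cases. Anyone who wants the number must assemble it from listings. The SAP states no rule for doing so, and its general specifications say that the outputs are unblinded.

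**Working it through.** The plan gives no figure to reproduce. The check sets the promise, the recording rule and the outputs side by side.

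**1. Is there an anaphylaxis output?** SAP Section 4 runs from Output 4.1 to Output 4.38 without a gap. None is a summary of anaphylaxis. The public copy omits some front pages of the SAP, but these come before the key definitions and do not interrupt the output list.

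**2. Can a preferred-term table supply the count?** The protocol's own example in 5.3.5.1, dyspnoea with hypotension, corresponds to items 2b and 2c of Appendix 6. It meets criterion 2 if the two occur rapidly after exposure to a likely allergen. On the eCRF it becomes two events, and in Outputs 4.7, 4.11, 4.13 and 4.14 it becomes two rows. Those tables count patients per term over the double-blind and follow-up periods. They do not show whether two signs belong to one patient or one episode.

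An illustration with invented counts: suppose the active arm (N = 69, SAP Output 1.1) has 5 patients with urticaria and 8 with dyspnoea. The number with both lies between

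- max(0, 5 + 8 − 69) = 0, and
- min(5, 8) = 5.

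Exact (Clopper-Pearson) 95% intervals at the two ends are:

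- 0/69 = 0%: 0 to 5.2% (upper limit 1 − 0.025^(1/69) = 0.052)
- 5/69 = 7.2%: 2.4 to 16.1%

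This shows what two marginal rows leave open. It is not a forecast, and the other outputs in steps 3 and 4 would narrow the range.

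**3. Can Output 4.15 supply it?** It gives the number of patients per arm with any AESI, but no row by type. The Grade 4 row is not a substitute. By the WHO scale in Appendix 7, ALT or AST above 3 × ULN, the Hy's Law entry level, falls in Grade 2 (2.6 to 5 × ULN), and higher values reach Grade 3 or 4. A Hy's Law case can therefore sit in Grade 2, 3 or 4. Where a reaction is entered as separate signs, each sign has its own grade, which need not be 4.

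**4. Can the discontinuation and serious-event outputs supply it?** Protocol 4.6.1 requires permanent discontinuation of treatment on suspicion of anaphylaxis or hypersensitivity to study drug. Life-threatening events are serious (5.2.2). Such cases should therefore reach Outputs 4.8 and 4.10 and Listings 4.33 and 4.34. The two tables use the Output 4.7 layout, so they show separate terms again. The listings allow a reader to rebuild cases by hand, without a stated rule.

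**5. What lies outside the recording rule?** A reaction starting more than 24 hours after dosing may be entered as a diagnosis (5.3.5.2) and would then appear as a term. Appendix 6 describes onset in minutes to several hours, so most anaphylaxis would be expected inside the window.

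**The case against.** The strongest reply is that anaphylaxis is well guarded in this trial. Investigators are to be trained in the criteria (5.1.1.2) and remain blinded (4.2). They must report these events immediately as AESIs, and as serious events where appropriate. Suspicion alone stops treatment. A case therefore leaves a trace in Outputs 4.8, 4.10 and 4.15 and in Listings 4.33 and 4.34, and Output 4.7 also has a Grade 3 and above subset. Phase I saw no anaphylaxis and no infusion-related reactions, though in healthy volunteers. On this view only a split of Output 4.15 by type is missing.

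Much of this stands. A reader might infer that anaphylaxis would go unnoticed or unreported, and the documents do not support that. Nor would a reader be right to infer that timing relative to dosing is confined to one listing: Listings 4.34 and 4.35 use the same layout as 4.32, so the short listing of treatment discontinuations carries it too. It would also be wrong to infer that no case definition exists, because Appendix 6 is one. What the SAP lacks is its application to the recorded signs.

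The reply does not close the gap. The traces are separate terms or a pooled AESI count, and the protocol promised a summary distinct from AESIs. The stopping rule depends on suspicion of the drug, so a cluster that the investigator attributes to asthma would not trigger it.

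The reply also corrects the obvious remedy. Grouping every sign within 24 hours of an infusion is looser than Appendix 6: urticaria at 1 hour and asthma dyspnoea at 23 hours would be joined. The grouping has to be tighter.

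**Conclusion.** The point holds as a gap between protocol and SAP with a real reporting consequence: a promised safety summary of a named risk is not planned, and no planned table gives the number of anaphylaxis patients per arm. It is a cheap improvement and not a flaw that undermines the trial. The cases themselves are captured, reported and, if suspected to be due to the drug, lead to stopping treatment.

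The documents give no basis for sizing the effect on a treatment comparison, because they state neither a background rate of such signs nor a reaction rate in patients with asthma. The 0 to 5 range above rests on invented counts and illustrates only what marginal term rows leave undetermined.

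The conclusion assumes that sites follow 5.3.5.1 as written and that no separate anaphylaxis output exists outside this SAP. The documents show none.

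**What to change.** Two additions to the SAP, with no new data collection:

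1. **Output 4.15:** add rows by AESI type (Hy's Law, infectious-agent transmission, Grade 3 or higher allergic reaction, with anaphylaxis shown within the last).
2. **One new table:** patients per arm with anaphylaxis, with exact 95% confidence intervals. A patient counts through either route:
   - an event reported as an anaphylaxis AESI; or
   - a cluster of signs after the same infusion that meets the Appendix 6 criteria, with the signs close together in time (minutes to several hours) and inside the 24-hour post-infusion window. The timing variable already specified for Listing 4.32 serves this purpose.

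Flagged clusters are confirmed by the sponsor's existing medical review, done without treatment codes. The SAP already carries arm sizes and specifies unblinded outputs, so the rule and the review should be documented before any cluster is looked at by arm.

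The cost is one derived flag, one table, a few extra rows and review of what should be a small number of episodes. It assumes that the AESI type can be identified from the eCRF or by the reviewer. The downside is false flags: asthma symptoms after an infusion can meet the respiratory item by chance, so the active count is read against placebo. Reactions starting after 24 hours stay in the general adverse-event tables unless reported as an anaphylaxis AESI.

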6.6 PHARMACOKINETIC ANALYSES

The PK analysis population will include patients with sufficient data to enable estimation of key parameters (e.g., peak serum concentration and predose trough concentrations). Serum study drug concentrations at selected timepoints will be tabulated and summarized by descriptive statistics. The extent of interpatient variability will be evaluated, and potential sources of variability will be assessed. Relationships between exposure and PD, efficacy, and safety endpoints will be explored.

Additional PK analyses will be conducted during and/or at the end of study as appropriate.

6.7 IMMUNOGENICITY ANALYSES

The immunogenicity analysis population will consist of all patients with at least one ADA assessment. Patients will be grouped according to treatment received or, if no treatment is received prior to study discontinuation, according to treatment assigned.

The numbers and proportions of ADA-positive patients and ADA-negative patients at randomization (baseline prevalence) and after drug administration (postbaseline incidence) will be summarized by treatment group. When determining postbaseline incidence, patients are considered to be ADA positive if they are ADA negative or have missing data at baseline but develop an ADA response following study drug exposure (treatment-induced ADA response), or if they are ADA positive at baseline and the titer of one or more postbaseline samples is at least 0.60 titer unit greater than the titer of the baseline sample (treatment-enhanced ADA response). Patients are considered to be ADA negative if they are ADA negative or have missing data at baseline and all postbaseline samples are negative, or if they are ADA positive at baseline but do not have any postbaseline samples with a titer that is at least 0.60 titer unit greater than the titer of the baseline sample (treatment unaffected).

The relationship between ADA status and safety, efficacy, PK, and biomarker endpoints will be analyzed and reported via descriptive statistics.

6.8 BIOMARKER ANALYSES

Biomarkers will be assessed to determine pharmacological activity and mechanism of action of MTPS9579A. Data will be summarized by absolute levels of the biomarker, as well as absolute and relative changes from randomization (defined as predose), for each treatment group. Additional PD analyses will be conducted as appropriate.

Potential predictive biomarkers of MTPS9579A response will be assessed in primary and key secondary endpoints (e.g., CompEx, asthma exacerbation rate) to assess if a subset of patients derives enhanced clinical benefit from MTPS9579A. Predictive biomarker candidates include, but are not limited to, blood eosinophils and germline mutations in the genes encoding tryptase (*TPSAB1* and *TPSB2*).

Further details related to biomarker analyses will be described in the DAP.

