2.5 BIOMARKER OBJECTIVE

The exploratory biomarker objective for this study is to identify and/or evaluate biomarkers that are predictive of response to MTPS9579A (i.e., predictive biomarkers), can provide evidence of MTPS9579A activity (i.e., PD biomarkers), or can increase the knowledge and understanding of disease biology and drug safety, on the basis of the following endpoints:

- Change from the randomization visit in biomarker levels in nasal mucosal lining fluid, urine, and serum samples
- Relationship among biomarker levels in nasal mucosal lining fluid, urine, and serum samples
- Relationship between biomarkers in nasal mucosal lining fluid, urine, and serum (listed in Section 4.5.9) and efficacy, safety, PK, and immunogenicity endpoints
- Rate of asthma exacerbations within subgroups defined by blood eosinophils during the 48-week double-blind treatment period
- Time to first CompEx event (as defined in primary efficacy objective) within subgroups defined by blood eosinophils during the 48-week double-blind treatment period
- Rate of asthma exacerbations in subgroups defined by mutations in the genes encoding tryptase (*TPSAB1* and *TPSB2*) during the 48-week double-blind treatment period
- Time to first CompEx event (as defined in primary efficacy objective) in subgroups defined by mutations in the genes encoding tryptase (*TPSAB1* and *TPSB2*) during the 48-week double-blind treatment period

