**BMI (kg/m2) at Baseline**

n nnn nnn nnn

Mean (SD) xx.x (xx.x) xx.x (xx.x) xx.x (xx.x)

Median xx.x xx.x xx.x

Min-max

xx.X

xx.X

xx.X

Geographic Region, IxRS Stratif

n

nnn

nnn

nnn

United States / Western Europe

xx.x (xx.x)

xx.x (xx.x)

xx.x (xx.x)

Eastern Europe

xx.X

xx.X

xx.X

Southern Hemisphere

xx.X

xx.X

xx.X

Asthma Exac in Prior Year, IxRS Stratif

n

nnn

nnn

nnn

1 event

xx.x (xx.x)

xx.x (xx.x)

xx.x (xx.x)

>=2 events

xx.X

xx.X

xx.X

Percent Predicted FEV1 at Baseline

n

nnn

nnn

nnn

Mean (SD)

xx.x (xx.x)

xx.x (xx.x)

xx.x (xx.x)

Median

xx.X

xx.X

xx.X

Min-max

xx.X

xx.X

xx.X

Blood Eosinophils at Baseline

n	nnn	nnn	nnn
Mean (SD)	xx.x (xx.x)	xx.x (xx.x)	xx.x (xx.x)
Median	xx.X	xx.X	xx.X
Min-max	xx.X	xx.X	xx.X
Blood Eosinophils Group at Baseline			
n	nnn	nnn	nnn
< 150	nn (xx.x%)	nn (xx.x%)	nn (xx.x%)
150 - 300	nn (xx.x%)	nn (xx.x%)	nn (xx.x%)
> 300	nn (xx.x%)	nn (xx.x%)	nn (xx.x%)
Active Tryptase Allele Counts			
n	nnn	nnn	nnn
<=2	xx.x (xx.x)	xx.x (xx.x)	xx.x (xx.x)
>2	xx.X	xx.X	xx.X
ACQ-5 Score at Baseline			
n	nnn	nnn	nnn
Mean (SD)	xx.x (xx.x)	xx.x (xx.x)	xx.x (xx.x)

Median	xx.x	xx.x	xx.x
Min-max	xx-xx	xx-xx	xx-xx

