Footnotes: Estimates are based on a mixed model for repeated measures (MMRM) analysis with an unstructured covariance matrix. The model used the absolute change pre-bronchodilator FEV1 as the response variable and included terms for treatment arm, study visit, treatment arm by study visit interaction, baseline FEV1 as well as its interaction with study visit, in addition to the stratification factors: blood eosinophil level at visit 1 (<150, >=150 to <=300, >300 cells/uL), number of asthma exacerbations requiring the use of systemic corticosteroids within the 12 months prior to the study entry (1 or >=2 events), and geographic region (United States/Western Europe [United States, Germany], Eastern Europe [Poland], Southern Hemisphere [Peru, Argentina]). Subjects without valid baseline values are excluded from analysis.

N in the header represents the number of subjects with at least one post-baseline value.

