## Section 5. Biomarker (PD) Analysis

The analyses of all PD endpoints will be based on the safety-evaluable population.

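### The predictive-biomarker aim has subgroup endpoints but no planned estimate of how the treatment effect differs by biomarker, so chance differences between small subgroups can easily look predictive

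*Protocol*

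**What the plan says.** Protocol Section 2.5 sets an exploratory objective that includes finding biomarkers predictive of response. Its efficacy endpoints are defined subgroup by subgroup. One is "Time to first CompEx event (as defined in primary efficacy objective) within subgroups defined by blood eosinophils during the 48-week double-blind treatment period", and exacerbation rate is listed in the same way. The same two outcomes are to be reported "in subgroups defined by mutations in the genes encoding tryptase".

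Section 6.8 states the purpose as "to assess if a subset of patients derives enhanced clinical benefit from MTPS9579A". The list of candidates is open: "Predictive biomarker candidates include, but are not limited to, blood eosinophils and germline mutations in the genes encoding tryptase". The method is deferred: "Further details related to biomarker analyses will be described in the DAP".

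The SAP does not take this up:

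- Its efficacy section (Section 3, Outputs 3.1 to 3.14) uses eosinophil level only as an adjustment covariate.
- Its only interactions are in the repeated-measures models, namely "treatment arm by study visit interaction" and baseline by visit (footnote to Output 3.6).
- Its biomarker section covers tryptase and urea over time: "The analyses of all PD endpoints will be based on the safety-evaluable population".
- The heading for biomarker subgroups under Key Definitions lists two sample types, nasosorption and serum.
- Genotype appears only as a row of the baseline table, "Active Tryptase Allele Counts", split at 2 (Output 2.1).

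**The concern.** Saying that a subset has enhanced benefit is a comparison: the treatment effect in one group against the effect in another. Separate hazard ratios by subgroup do not estimate that comparison. A reader shown a favourable hazard ratio in one eosinophil group and a neutral one in the next will tend to see a predictive marker, although the two intervals may overlap almost completely.

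The trial is small for this purpose. It has 134 treated patients, an open list of candidates and no multiplicity adjustment. What is at stake is candidate selection. A chance pattern could be carried forward as a hypothesis about who responds, or a real modifier could be lost among equally large chance patterns.

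**Working it through.** **The plan's own figure.** There is none to reproduce. Protocol Section 6.1 refers to 51 events and reasonable precision, and the text after that is redacted. What follows is a substitute calculation.

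**Inputs**
- Patients: 134 in the modified intent-to-treat set, 65 placebo and 69 active (SAP Output 1.1); 1:1 randomisation (Protocol Section 4.2).
- Events: about 51 at the planned interim analysis (Section 6.9.1). The final number is not stated. Assumed range D = 51 to 90, that is 51/134 = 38% to 90/134 = 67% of patients.
- Groups, for illustration: three eosinophil groups (the categories in Protocol Sections 4.2 and 6.4) and two tryptase groups (the baseline-table split), with events divided equally. The enrolment caps of about 35% per eosinophil group correspond to 0.35 x 134 = 47 patients.
- Test level: two-sided 0.2, which Protocol Section 6 sets for primary and secondary tests. Carrying it over to subgroups is an assumption.

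**Step 1: precision of one subgroup.** SE(log HR) = 2/sqrt(d), with d events in the group; the 95% interval is HR divided and multiplied by exp(1.96 x SE).

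| D | d (three groups) | SE | factor | d (two groups) | SE | factor |
|---|---|---|---|---|---|---|
| 51 | 17 | 0.485 | 2.59 | 25.5 | 0.396 | 2.17 |
| 70 | 23.3 | 0.414 | 2.25 | 35 | 0.338 | 1.94 |
| 90 | 30 | 0.365 | 2.05 | 45 | 0.298 | 1.79 |

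**Step 2: chance of a two-fold spread when the true HR is the same everywhere.** For two groups, the difference in log HR has SE 4/sqrt(D), so P = 2[1 - Φ(ln 2 / (4/sqrt(D)))]. At D = 51 this is 2[1 - Φ(0.693/0.560)] = 0.216. For three groups, the highest and lowest of three independent normal log HRs were simulated 400,000 times.

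| D | three groups | two groups |
|---|---|---|
| 51 | 57% | 22% |
| 70 | 46% | 15% |
| 90 | 37% | 10% |

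**Step 3: chance that some but not all of three groups show nominal benefit at 0.2.** If each group does so with probability p, the chance is 1 - (1 - p)^3 - p^3.
- True HR 1.0: p = 0.1, giving 1 - 0.729 - 0.001 = 0.27 at any D.
- True HR 0.7 in every group: p = Φ(0.357/SE - 1.282). At D = 51, p = Φ(-0.546) = 0.292, giving 1 - 0.354 - 0.025 = 0.62. The simulation gives 62%, 67% and 71% at D = 51, 70 and 90.

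The pattern is therefore more likely when the drug works equally well in every group than when it does nothing.

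**Step 4: what an interaction term does.** With no true heterogeneity, a test of equal effects at 0.2 is positive in about 20% of trials, whatever the common HR (simulated 19.9% to 20.1%). For two equal groups and a true two-fold ratio of HRs, power is Φ(0.693/(4/sqrt(D)) - 1.282), or 48%, 57% and 64% at D = 51, 70 and 90. At alpha 0.05 it is 24%, 30% and 38%. The 95% interval for the ratio of HRs spans a factor exp(1.96 x 4/sqrt(D)) either way: 3.00, 2.55 and 2.29.

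**The case against.** The best defence is that the plan has not chosen the wrong method; it has not stated one. Section 2.5 lists endpoints, Section 6.8 defers the analysis, and nothing excludes an interaction model. The SAP is a set of output shells limited to primary and secondary efficacy. It is equally silent on other exploratory outcomes such as methacholine response, diary symptom scores and rescue use, so the gap is not peculiar to biomarkers. The objective is labelled exploratory and the study hypothesis-generating. An interaction test would also have low power.

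Most of this stands, and it rules out some stronger readings:

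- A reader might infer that subgroup hazard ratios were chosen in preference to an interaction. The text does not say so.
- A reader might infer that the eosinophil categories and the allele split will define the efficacy subgroups, discarding the measured values. No section applies either cut to efficacy. The eosinophil categories serve as enrolment caps, covariate levels and a baseline row, and the allele split is a baseline row only.
- A reader might infer that enrichment of a next study will rest on these subgroups. Planning of future studies is mentioned as a use of the interim analyses, not of the biomarker subgroups.

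What the defence does not remove is the consequence. The only predictive efficacy analyses named in either document are outcomes by subgroup. Carrying out what is written yields separate, imprecise estimates and no estimate of the difference between them.

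**Conclusion.** The concern holds as a gap with a cheap remedy, not as an error that undermines the trial. Neither document plans an estimate of how the treatment effect varies with a biomarker, and at this size subgroup results can easily mislead. It would go too far to say that they will.

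The likelihood depends on the number of groups and events. A two-fold spread by chance is common with three eosinophil groups (57% to 37%) and less so with two tryptase groups (22% to 10%). Nominal benefit in some but not all eosinophil groups arises in 27% of trials if the drug has no effect and in 62% to 71% if the true HR is 0.7 throughout.

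These figures rest on 51 to 90 events, equal splits, alpha 0.2 carried over to subgroups, and normal approximations for CompEx. Exacerbation rate was not quantified. Splits may be unequal: if the 35% caps apply to the planned 160 patients (56 per group), two full groups would leave 134 - 112 = 22 patients in the third, with a still less precise estimate there.

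It would be equally wrong to make a significant interaction the sole gate for calling a marker predictive. With power of 48% to 64% for a two-fold ratio, real modifiers would often be missed.

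**What to change.** In Protocol Section 6.8 and the SAP, add outputs for two biomarkers, blood eosinophils and active tryptase allele count:

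- Fit the planned Cox model (CompEx) and the planned over-dispersed Poisson model (exacerbation rate) in all patients, with treatment, biomarker and treatment-by-biomarker terms.
- Use the measured value where possible, for example log eosinophils and the allele count as a number. Use the subgroup display to check whether a monotone trend is reasonable.
- Name one eosinophil measurement. The opening of SAP Section 3 uses Week 2, while Protocol Section 6.4 and the footnote to SAP Output 3.1 use Visit 1; these need to be reconciled.
- Report the interaction ratio (of hazard ratios or rate ratios) with its confidence interval beside the subgroup estimates, and mark the latter as descriptive.
- Label the analysis exploratory and state how many biomarkers were examined. With two independent markers tested at 0.2, the chance of at least one false positive is 1 - 0.8^2 = 0.36.
- State that no predictive claim will rest on subgroup estimates alone, and that a null interaction will not be read as evidence of a homogeneous effect.

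If treatment results by biomarker have been seen before this is added, say so. The cost is SAP wording and four model fits (two biomarkers by two outcomes) on data already being collected.
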